#### **5.3.5.7      Abnormal Vital Sign Values**

Not every vital sign abnormality qualifies as an adverse event. A vital sign result must be reported as an adverse event if it meets any of the following criteria:

- Is accompanied by clinical symptoms
- Results in a change in study treatment (e.g., dosage modification, treatment interruption, or treatment discontinuation)
- Results in a medical intervention or a change in concomitant therapy
- Is clinically significant in the investigator's judgment

It is the investigator's responsibility to review all vital sign findings. Medical and scientific judgment should be exercised in deciding whether an isolated vital sign abnormality should be classified as an adverse event.

If a clinically significant vital sign abnormality is a sign of a disease or syndrome (e.g., high blood pressure), only the diagnosis (i.e., hypertension) should be recorded on the Adverse Event eCRF.

Observations of the same clinically significant vital sign abnormality from visit to visit should only be recorded once on the Adverse Event eCRF (see Section [5.3.5.5](#) for details on recording persistent adverse events).

#### **5.3.5.8      Abnormal Liver Function Tests**

The finding of an elevated ALT or AST ( $>3 \times \text{ULN}$ ) in combination with either an elevated total bilirubin ( $>2 \times \text{ULN}$ ) or clinical jaundice in the absence of cholestasis or other causes of hyperbilirubinemia is considered to be an indicator of severe liver injury (as defined by Hy's Law). Therefore, investigators must report as an adverse event the occurrence of either of the following:

- Treatment-emergent ALT or AST  $>3 \times \text{ULN}$  in combination with total bilirubin  $>2 \times \text{ULN}$
- Treatment-emergent ALT or AST  $>3 \times \text{ULN}$  in combination with clinical jaundice

The most appropriate diagnosis or (if a diagnosis cannot be established) the abnormal laboratory values should be recorded on the Adverse Event eCRF (see Section 5.3.5.3) and reported to the Sponsor immediately (i.e., no more than 24 hours after learning of the event), either as a serious adverse event or an adverse event of special interest (see Section 5.4.2).

### **5.3.5.9 Deaths**

All deaths that occur during the protocol-specified adverse event reporting period (see Section 5.3.1), regardless of relationship to study drug, must be recorded on the Adverse Event eCRF and immediately reported to the Sponsor (see Section 5.4.2). This includes death attributed to progression of ulcerative colitis or Crohn's disease.

Death should be considered an outcome and not a distinct event. The event or condition that caused or contributed to the fatal outcome should be recorded as the single medical concept on the Adverse Event eCRF. Generally, only one such event should be reported. If the cause of death is unknown and cannot be ascertained at the time of reporting, "unexplained death" should be recorded on the Adverse Event eCRF. If the cause of death later becomes available (e.g., after autopsy), "unexplained death" should be replaced by the established cause of death. The term "**sudden death**" should not be used unless combined with the presumed cause of death (e.g., "sudden cardiac death").

If the death is attributed to progression of UC or CD, "ulcerative colitis or Crohn's disease progression" should be recorded on the Adverse Event eCRF.

Deaths that occur after the adverse event reporting period should be reported as described in Section 5.6.

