### **5.3.1 Adverse Event Reporting Period**

Investigators will seek information on adverse events at each patient contact.

All adverse events, whether reported by the patient or noted by study personnel, will be recorded in the patient's medical record and on the Adverse Event eCRF.

After informed consent has been obtained but prior to initiation of study drug, only serious adverse events caused by a protocol-mandated intervention (e.g., invasive procedures such as biopsies, discontinuation of medications) should be reported (see [Section 5.4.2](#) for instructions for reporting serious adverse events).

After initiation of study drug, all adverse events will be reported regardless of relationship to study drug, up until the patient completes his or her last study visit (in the Safety Follow-Up Phase) or 12-weeks after the last study drug administration whichever is longer. After the Safety Follow-Up Phase, the investigator should report any serious adverse events that are believed to be related to prior study drug treatment (see [Section 5.6](#)). In addition, the Sponsor should be notified if the investigator becomes aware of any post-study events of confirmed or suspected PML, regardless of relationship to study drug, for up to 2 years after the patient's last dose of study drug (see [Section 5.6](#)).

Instructions for reporting adverse events that occur after the adverse event reporting period are provided in [Section 5.6](#).

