## **5.6 ADVERSE EVENTS THAT OCCUR AFTER THE ADVERSE EVENT REPORTING PERIOD**

The Sponsor should be notified if the investigator becomes aware of any serious adverse event that occurs after the end of the adverse event reporting period (defined as 12 weeks after the last dose of study drug, see Section 5.3.1) if the event is believed to be related to prior study drug treatment. In addition, the Sponsor should be notified if the investigator becomes aware of any post-study events of confirmed or suspected

progressive multifocal leukoencephalopathy, regardless of relationship to study drug, for up to 2 years after the patient's last dose of study drug. These events should be reported through use of the Adverse Event eCRF. However, if the EDC system is not available, the investigator should report these events directly to the Sponsor or its designee, either by faxing or by scanning and emailing the paper Clinical Trial Serious Adverse Event/Adverse Event of Special Interest Reporting Form using the fax number or email address provided to investigators.

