- g For patients that complete the OLE *treatment*, the PML monitoring phase includes 104 weeks of PML safety monitoring.
- h Unscheduled visit represents a visit that is not as per Schedule of Assessments and it is symptom driven.
- i If there are any signs or symptoms suggestive of PML identified on the subjective checklist during the telephone call, the patient will be asked to come into the clinic for further evaluation and if indicated referral to a neurologist. .
- j Investigators are not required to actively monitor patients for adverse events; however, if he or she becomes aware of any other serious adverse events that are believed to be related to prior study drug treatment, these should be reported directly to Roche or its designee either by faxing or by scanning and e-mailing the Serious Adverse Event/Adverse Event of Special Interest Reporting Form with use of the fax number or e-mail address provided to the investigators. The investigator may become aware of such events at these timepoints or via other means, but the data are not to be collected routinely.

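### Section 5.3.5.9 sends all late deaths to Section 5.6, which gives no reporting route for a death judged unrelated and not suspected to be PML

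*Combined protocol and SAP*

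**What the plan says.** Inside the reporting period the rule is complete. Section 5.3.5.9: "All deaths that occur during the protocol-specified adverse event reporting period (see Section 5.3.1), regardless of relationship to study drug, must be recorded". Death is treated there as an outcome, and the condition that caused it is entered as the event term. For later deaths the same section gives only a cross-reference: "Deaths that occur after the adverse event reporting period should be reported as described in Section 5.6".

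Section 5.6 contains two rules and no text on deaths:

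- Serious adverse events that the investigator becomes aware of are notified "if the event is believed to be related to prior study drug treatment".
- Confirmed or suspected PML is notified separately. That rule covers "progressive multifocal leukoencephalopathy, regardless of relationship to study drug, for up to 2 years after the patient's last dose of study drug".

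Section 5.3.1 repeats both rules. Appendix 1e, footnote j, which governs the PML monitoring phase, repeats the first and adds: "Investigators are not required to actively monitor patients for adverse events".

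The sections also differ on when the reporting period ends. Section 5.6 has it "defined as 12 weeks after the last dose of study drug, see Section 5.3.1", and Section 5.4.2.2 agrees. Section 5.3.1 itself says the last safety follow-up visit "or 12-weeks after the last study drug administration whichever is longer".

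**The concern.** The cross-reference reads as if it settles how every late death is reported. The section it leads to filters on the site's causality opinion, with PML as the one exception. A child in PML monitoring is still in a study phase, and that phase exists to detect a disease the protocol calls potentially fatal. If such a child dies and the site attributes the death to something else, the sponsor need not receive the cause of death, a causality assessment, or a statement of whether PML was considered. The attribution then rests with the site and is not reviewed. With about 24 children planned, one such death would matter to any account of this phase.

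**Working it through.** **Step 1. Trace each kind of late death through the text.** The inputs are Section 5.2.2 (a fatal event is serious), Section 5.3.5.9 (death is an outcome of a causing event), Table 6 (an event counts as related unless there is evidence of another cause or no plausible timing), and Section 5.6.

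| Death after the reporting period | Rule that applies | Report required? |
|---|---|---|
| Cause believed related to study drug | Section 5.6, first rule, because a fatal event is serious | Yes |
| Confirmed or suspected PML, any relationship | Section 5.6, second rule, up to 2 years after last dose | Yes |
| Unexplained | Table 6 defaults to related, so the first rule tends to apply | Usually yes |
| Attributed by the site to another cause, PML not suspected | Neither rule | No |

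The last row is the gap. The third row is not watertight. Table 6 allows a judgment of unrelated where timing is implausible, and Section 5.1.1.7 equates about 2.5 months with roughly 5 half-lives. A site could reasonably use that exit for a death more than 12 weeks after the last dose.

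**Step 2. Look for another place that would catch it.** Section 4.6.2 has the primary reason for study withdrawal entered on an eCRF, and Section 6.2 has those reasons listed and summarised. A known death could appear there. Neither section specifies a cause of death, a causality assessment or a statement on PML.

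**Step 3. Measure how much of PML monitoring is affected.** Count the 104 weeks from the last dose, as Section 4.5 does in setting PML follow-up at 2 years after the last dose.

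- Section 5.6 cut-off of 12 weeks: 104 − 12 = 92 weeks; 92/104 = 88.5%.
- Section 5.3.1, Q4W completer (last dose Week 12, last safety visit Week 24): 24 − 12 = 12 weeks, so again 92/104 = 88.5%.
- Section 5.3.1, Q8W completer (last dose Week 8, last safety visit Week 24): 24 − 8 = 16 weeks; 104 − 16 = 88 weeks; 88/104 = 84.6%.

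Appendix 1e places the last call for treatment-phase completers 92 weeks after Week 24, which is Week 116. For a Q8W completer that is 116 − 8 = 108 weeks after the last dose. On that count the shares are 92/108 = 85.2% (Section 5.3.1) and 96/108 = 88.9% (Section 5.6), a shift of less than one percentage point.

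**Step 4. Spacing of contacts.** Appendix 1e schedules calls at Weeks 24, 48, 68 and 92, so the gaps are 24, 24, 20 and 24 weeks. A child could deteriorate and die between two calls with no positive checklist on record.

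**The case against.** The best defence is that the filter is deliberate. It appears consistently in Sections 5.3.1 and 5.6 and in Appendix 1e. The 12-week cut-off lies just beyond the roughly 2.5 months that the protocol equates with about 5 half-lives. Mortality is not an objective or endpoint. The disease of interest has its own rule: suspicion alone makes PML reportable. Caregivers hold alert cards asking them to contact the investigator promptly about new neurological problems, and symptom-driven calls and visits are available between scheduled ones.

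Most of this stands, and it rules out several stronger readings.

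- A reader might infer that Section 5.6 asks only for drug-related events. Its next sentence contradicts that: "In addition, the Sponsor should be notified if the investigator becomes aware of any post-study events of confirmed or suspected" PML, whatever the relationship.
- A reader might infer that a late unrelated death is never reported. The text only fails to require it. A site may report it voluntarily, and the withdrawal form may show it.
- A reader might infer that an unreported death is counted as free of PML. No section says how deaths are classified for the PML endpoint.
- A reader might size the problem by the upper confidence bound on the PML rate when no case is seen. That bound depends on the number followed and is the same whether or not deaths are reported, so it does not measure this gap.

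The defence does not supply an instruction for the last row of the table. Section 5.3.5.9 tells the site that late deaths are to be reported, and the section it names is silent for that case. The PML rule helps only if someone suspects PML.

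**Conclusion.** The point holds as a limited gap. A death that the site attributes to another cause and does not suspect to be PML has no required safety report after the reporting period. That covers about 85% to 88% of the 104-week PML monitoring period (88 to 92 weeks, depending on which end of the reporting period applies). Deaths believed related and deaths from confirmed or suspected PML are covered, and unexplained deaths mostly are.

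The share assumes the 104 weeks are counted from the last dose and that the child stays in monitoring throughout. Some sections only offer this phase, so the number followed may be below the approximately 24 planned. The documents give no mortality rate. Assuming 0 to 1 deaths in this phase, the practical weight lies in whether a single death would reach the sponsor with its cause. The change is worth making because it is cheap, although no planned analysis fails without it.

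**What to change.** - In Section 5.6, Section 5.3.1 and Appendix 1e, footnote j, state that every death the investigator learns of up to the end of PML monitoring is recorded on the Adverse Event eCRF regardless of relationship, with date, cause and whether PML was excluded.
- Record vital status at the PML calls already scheduled.
- When summarising the PML endpoint, list separately any death in which PML was not excluded.
- In the same edit, reconcile the end of the reporting period in Section 5.3.1 with the 12 weeks in Sections 5.6 and 5.4.2.2.

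The cost is a sentence in three places, one item at existing calls and at most a few extra reports. No new visit, sample or form is needed.

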### **5.3.5.10 Preexisting Medical Conditions**

A preexisting medical condition is one that is present at the screening visit for this study. Such conditions should be recorded on the General Medical History and Baseline Conditions eCRF.

A preexisting medical condition should be recorded as an adverse event only if the frequency, severity, or character of the condition worsens during the study. When recording such events on the Adverse Event eCRF, it is important to convey the concept that the preexisting condition has changed by including applicable descriptors (e.g., "more frequent headaches").

### **5.3.5.11 Lack of Efficacy or Worsening of Ulcerative Colitis or Crohn's Disease**

Medical occurrences or symptoms of deterioration that are anticipated as part of ulcerative colitis or Crohn's disease should be recorded as an adverse event if judged by the investigator to have unexpectedly worsened in severity or frequency or changed in nature at any time during the study. When recording an unanticipated worsening of ulcerative colitis or Crohn's disease on the Adverse Event eCRF, it is important to

convey the concept that the condition has changed by including applicable descriptors (e.g., "accelerated worsening of ulcerative colitis or Crohn's disease").

#### **5.3.5.12 Hospitalization or Prolonged Hospitalization**

Any adverse event that results in hospitalization (i.e., inpatient admission to a hospital) or prolonged hospitalization should be documented and reported as a serious adverse event (per the definition of serious adverse event in Section 5.2.2), except as outlined below.

An event that leads to hospitalization under the following circumstances should not be reported as an adverse event or a serious adverse event:

- Hospitalization for respite care
- Planned hospitalization required by the protocol (e.g., for study drug administration or insertion of access device for study drug administration)
- Hospitalization for a preexisting condition, provided that all of the following criteria are met:
  - The hospitalization was planned prior to the study or was scheduled during the study when elective surgery became necessary because of the expected normal progression of the disease.

The patient has not experienced an adverse event.

The following hospitalization scenarios are not considered to be serious adverse events, but should be reported as adverse events instead:

- Hospitalization that was necessary because of patient requirement for outpatient care outside of normal outpatient clinic operating hours

#### **5.3.5.13 Adverse Events Associated with an Overdose or Error in Drug Administration**

An overdose is the accidental or intentional use of a drug in an amount higher than the dose being studied. An overdose or incorrect administration of study treatment is not itself an adverse event, but it may result in an adverse event. All adverse events associated with an overdose or incorrect administration of study drug should be recorded on the Adverse Event eCRF. If the associated adverse event fulfills seriousness criteria, the event should be reported to the Sponsor immediately (i.e., no more than 24 hours after learning of the event; see Section 5.4.2).

Any study drug overdose or incorrect administration of study drug should be noted on the Study Drug Administration eCRF.

#### **5.3.5.14 Clinical Outcomes Assessment Data**

Adverse event reports will not be derived from COA data by the Sponsor, and safety analyses will not be performed using COA data. However, if any COA responses suggestive of a possible adverse event are identified during site review of the COA data,

the investigator will determine whether the criteria for an adverse event have been met and, if so, will report the event on the Adverse Event eCRF.

## **5.4 IMMEDIATE REPORTING REQUIREMENTS FROM INVESTIGATOR TO SPONSOR**

Certain events require immediate reporting to allow the Sponsor to take appropriate measures to address potential new risks in a clinical trial. The investigator must report such events to the Sponsor immediately; under no circumstances should reporting take place more than 24 hours after the investigator learns of the event. The following is a list of events that the investigator must report to the Sponsor within 24 hours after learning of the event, regardless of relationship to study drug:

- Serious adverse events (defined in Section 5.2.2; see Section 5.4.2 for details on reporting requirements)
- Adverse events of special interest (defined in Section 5.2.3; see Section 5.4.2 for details on reporting requirements)
- Pregnancies (see Section 5.4.3 for details on reporting requirements)

The investigator must report new significant follow-up information for these events to the Sponsor immediately (i.e., no more than 24 hours after becoming aware of the information). New significant information includes the following:

- New signs or symptoms or a change in the diagnosis
- Significant new diagnostic test results
- Change in causality based on new information
- Change in the event's outcome, including recovery
- Additional narrative information on the clinical course of the event

Investigators must also comply with local requirements for reporting serious adverse events to the local health authority and IRB/EC.

#### **5.4.2 Reporting Requirements for Serious Adverse Events, Adverse Events of Special Interest**

##### **5.4.2.1 Events That Occur prior to Study Drug Initiation**

After informed consent has been obtained but prior to initiation of study drug, only serious adverse events caused by a protocol-mandated intervention should be reported. The paper Clinical Trial Serious Adverse Event/Adverse Event of Special Interest Reporting Form provided to investigators should be completed and submitted to the Sponsor or its designee immediately (i.e., no more than 24 hours after learning of the event), either by faxing or by scanning and emailing the form using the fax number or email address provided to investigators.

##### **5.4.2.2 Events That Occur after Study Drug Initiation**

After initiation of study drug, serious adverse events and adverse events of special interest will be reported until 12 weeks after the last dose of study drug. Investigators should record all case details that can be gathered immediately (i.e., within 24 hours after learning of the event) on the Adverse Event eCRF and submit the report via the electronic data capture (EDC) system. A report will be generated and sent to Safety Risk Management by the EDC system.

In the event that the EDC system is unavailable, the paper Clinical Trial Serious Adverse Event/Adverse Event of Special Interest Reporting Form provided to investigators should be completed and submitted to the Sponsor or its designee immediately (i.e., no more than 24 hours after learning of the event), either by faxing or by scanning and emailing the form using the fax number or email address provided to investigators. Once the EDC system is available, all information will need to be entered and submitted via the EDC system.

Instructions for reporting serious adverse events that occur more than 12 weeks after the last dose of study treatment are provided in Section [5.6](#).

#### **5.4.3 Reporting Requirements for Pregnancies**

##### **5.4.3.1 Pregnancies in Female Patients**

Female patients of childbearing potential will be instructed *through the Informed Consent Form* to immediately inform the investigator if they become pregnant during the study or within 24 weeks after the last dose of study drug. A paper Clinical Trial Pregnancy Reporting Form should be completed and submitted to the Sponsor or its

designee immediately (i.e., no more than 24 hours after learning of the pregnancy), either by faxing or by scanning and emailing the form using the fax number or email address provided to investigators. Pregnancy should not be recorded on the Adverse Event eCRF. The investigator should discontinue study drug and counsel the patient, discussing the risks of the pregnancy and the possible effects on the fetus. Monitoring of the patient should continue until conclusion of the pregnancy. Any serious adverse events associated with the pregnancy (e.g., an event in the fetus, an event in the mother during or after the pregnancy, or a congenital anomaly/birth defect in the child) should be reported on the Adverse Event eCRF. In addition, the investigator will submit a Clinical Trial Pregnancy Reporting Form when updated information on the course and outcome of the pregnancy becomes available.

